5.1.4 Discontinuation of Study Therapy

Subjects MUST be discontinued from study therapy AND withdrawn from the study for the following reasons:

- Withdrawal of informed consent (subject's decision to withdraw for any reason)
- Any clinical adverse event, laboratory abnormality or intercurrent illness which, in the opinion of the investigator, indicates that continued treatment with study therapy is not in the best interest of the subject
- Termination of the study by Bristol-Myers Squibb (BMS).
- Imprisonment or the compulsory detention for treatment of either a psychiatric or physical (e.g., infectious disease) illness.
- Progression of disease, as defined by radiographic progression, **after 12 weeks of therapy**. Furthermore, all radiographic progression must be confirmed by a repeat scan done at least 4 weeks after the suspicious scan. Immune response is not a part of this algorithm.

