For weeks 12-24, patients are observed for progression.

Patients who do not progress by week 24 will receive ipilimumab 10 mg/kg IV every three months for weeks 24-60.

Patients will be followed for 5 years after completion of study treatment

PROTOCOL SYNOPSIS

Protocol Title:	A Phase II Study of CTLA Blockade by Ipilimumab plus Androgen Suppression Therapy in Patients with an Incomplete Response to AST Alone for Metastatic Prostate Cancer			
Site Numbers & Names:	This study is currently open at Oregon Health & Science University and Rutgers Cancer Institute of New Jersey.			
Research Hypothesis:	The early addition of immunotherapy in patients with metastatic prostate cancer who have a poor prognosis as a result of an incomplete biochemical response to androgen suppression therapy (AST) will improve outcomes to approximate outcomes in patients who do obtain a complete biochemical response with AST.			
Study Schema: Drugs / Doses / Length of Treatment)	All patients will receive ipilimumab 10 mg/kg by 90-minute IV infusion every three weeks for four doses. Patients without progression at Week 24 will subsequently receive maintenance ipilimumab 10 mg/kg IV every 12 weeks for four additional doses. Patients will have their PSA checked every three weeks during the first four doses of ipilimumab, every six weeks between weeks 12 and 24, and every 12 weeks thereafter. Once all eight doses of ipilimumab have been given, patients will be followed with a serum PSA every 12 weeks (either at the research site or at the patient's treating physician) until radiographic progression. Survival status will be assessed by telephone every 6 months for as long as patients are alive for up to 5 years after their last study visit. There will be a CT scan of the chest/abdomen/pelvis and whole body bone scans at baseline, 12 weeks, 24 weeks, and then every three months until radiographic progression. Scans may be performed sooner if there are any concerns about progression. Correlative study labs will be drawn just prior to ipilimumab administration during the first four doses (weeks 1, 4, 7, 10).			

Study Objectives:	The primary endpoint is the proportion of patients who achieve an undetectable PSA (≤ 0.2 ng/ml) after initiation of ipilimumab therapy.

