2.2 Secondary Objectives

- Time to PSA progression
- Time to progression by any measure
- Maximum percentage of PSA reduction in each patient
- Number of patients with IRAEs and correlation of these with complete PSA response, time to progression, and T cell measurements
- Measures of T cell response to therapy with flow cytometry
- Response in Measurable disease by modified RECIST criteria
- Time to death from any cause.
- To examine correlative biomarkers and their relationship to clinical outcomes. Potential biomarkers include, but are not limited to CRP, IGF-1 and -2, or FSH.
- Bank samples for future molecular correlative studies, biomarker, or other studies.

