3.6 Follow-up visits after completion of ipilimumab therapy

Patients will be followed with a history, physical exam, CT and NM bone scan and serum PSA quarterly along with treatment visits during the maintenance treatment phase, until radiographic progression. If a patient has not met radiographic progression by Week 60 visit, the patient will be followed by PSA and scans until radiographic progression. Following radiographic progression, patients will be followed by semi-annual phone surveys with the patient, his family, or his treating physician to collect data on treatment status and overall survival for up to 5 years after all protocol treatment has been completed.

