5.1.5 Permanent Discontinuation of Ipilimumab

5.1.5.1 Permanent Discontinuation for Related Adverse Events

- Any ≥ Grade 2 eye pain or reduction of visual acuity that does not respond to topical therapy and does not improve to ≤ Grade 1 severity within 2 weeks of starting therapy, OR, requires systemic treatment.
- Any \geq Grade 3 bronchospasm or other hypersensitivity reaction.
- Any other \geq Grade 3 non-skin related adverse event with the exception of events listed under "No Discontinuation" (below).
- Any adverse event, laboratory abnormality or intercurrent illness which, in the judgment of the investigator, presents a substantial clinical risk to the patient with continued dosing.

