6.2.1 Study Completion or Early Discontinuation Visit

At the time of study early withdrawal, the reason for early withdrawal and any new or continuing adverse events should be documented.

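### Section 5.1.4 withdraws men from the study at confirmed radiographic progression or for toxicity, contradicting the follow-up ordered elsewhere; where a site applies it, later survival and PSA data are lost

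*Combined protocol and SAP*

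**What the plan says.** Section 5.1.4 opens with a mandatory double instruction: "Subjects MUST be discontinued from study therapy AND withdrawn from the study for the following reasons". Two of its five reasons matter here. One is toxicity or illness: "Any clinical adverse event, laboratory abnormality or intercurrent illness which, in the opinion of the investigator, indicates that continued treatment" is not in the man's interest. The other is "Progression of disease, as defined by radiographic progression" after 12 weeks, confirmed on a repeat scan. The other three are withdrawal of consent, termination of the study, and imprisonment or compulsory detention.

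Other sections order follow-up of the same men:

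- **Section 3.6:** "Following radiographic progression, patients will be followed by semi-annual phone surveys with the patient, his family, or his treating physician", for up to 5 years after protocol treatment.
- **Synopsis:** survival status every 6 months "for as long as patients are alive for up to 5 years after their last study visit".
- **Section 6.4.2:** telephone survival surveys every 6 months for at most 5 years.
- **Section 6.1, footnote 4:** PSA continues until radiographic progression, with no toxicity exception.
- **Section 7.3.1:** serious adverse events are collected for 70 days after dosing stops.

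Section 5.1.5.1, headed "Permanent Discontinuation for Related Adverse Events", stops ipilimumab and does not mention leaving the study. For early withdrawal, 6.2.1 asks only this: "At the time of study early withdrawal, the reason for early withdrawal and any new or continuing adverse events should be documented".

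On analysis, 2.2 lists "Time to death from any cause" as a secondary objective. Section 8.5 censors it for loss to follow-up only. Section 8.4 uses the intention-to-treat population on condition that the endpoints were measured.

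**The concern.** A mandatory instruction that joins the end of treatment to the end of study participation cannot be read alongside a requirement to follow the same man after the same event. The conflict would reach the analysis in three ways.

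- **Time to death.** Men would be censored at progression. If the hazard of death rises at that point, the censoring is informative and the Kaplan-Meier curve is expected to lie too high.
- **PSA endpoints.** A man withdrawn for toxicity during induction would have no week 12, 18 or 24 PSA. The success rule in 8.3 is judged at 6 months, and 6.4.4 says immune activation may take weeks to months to show.
- **Correlation of IRAEs with outcome.** The missing PSA and progression data would fall on men with IRAEs, the group that this objective examines.

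Section 8.5 says nothing about men withdrawn by rule. Under 8.4 they could be dropped as unmeasured or counted as non-responders, depending on who does the analysis.

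**Working it through.** **1. The passages side by side**

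| Event | 5.1.4 | Elsewhere |
|---|---|---|
| Confirmed radiographic progression after 12 weeks | Off drug and off study | Survival calls up to 5 years (3.6; synopsis and 6.4.2 in general terms) |
| Adverse event or illness, by investigator opinion | Off drug and off study | Off drug only, for listed related events (5.1.5.1); PSA until progression (6.1, footnote 4); SAEs for 70 days (7.3.1) |

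The first row concerns the same men at the same event. In the second row the sections overlap without being identical, because 5.1.4 turns on opinion and 5.1.5.1 on listed events. I attribute no PSA loss to withdrawal at progression, since footnote 4 stops PSA there anyway.

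**2. The plan's own figure**

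Section 8.3 continues if at least 2 of the first 10 men respond and declares success at 6 or more of 30, with rates of 10% and 30%. The probability of success at rate p is the sum over x = 2 to 10 of P(X1 = x) × P(X2 ≥ 6 − x), where X1 ~ Bin(10, p) and X2 ~ Bin(20, p). At p = 0.30 this is 0.815, against the stated 80%. At p = 0.10 it is 0.0525, against the stated 0.05. This point does not depend on the small difference in type I error.

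**3. How many men toxicity might touch**

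The documents give no withdrawal rate. The proxies are:

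- Grade 3-4 irAEs at 10 mg/kg in the melanoma trial (Table 1): 30 × 0.254 = 7.6 men. The central 95% of Bin(30, 0.254) runs from 3 to 12.
- Serious IRAEs across the programme (1.3.5), about 15%: 30 × 0.15 = 4.5.
- Drug-related SAEs at 10 mg/kg (1.3.4.2), 26%: 30 × 0.26 = 7.8.

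The interval of 3 to 12 covers binomial variation only. It does not cover the step from event to withdrawal.

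**4. What that could do to the primary test**

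*Counted as non-responders.* Let t be the proportion withdrawn and f the share of their responses that would have come after withdrawal (assumed). Take toxicity as unrelated to response. The effective rate is 0.30 × (1 − t × f).

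| t | f | Effective rate | Power |
|---|---|---|---|
| 0.15 | 0.25 | 0.289 | 0.79 |
| 0.254 | 0.50 | 0.262 | 0.71 |
| 0.254 | 1.00 | 0.224 | 0.56 |

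*Dropped as unmeasured.* The proxies leave about 30 − 7.8 = 22 to 30 − 4.5 = 26 men (rounded). With the cut-off kept at 6 and all losses placed in stage 2, power is 0.65 (22 men), 0.71 (24) and 0.76 (26).

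**5. What withdrawal at progression could do to time to death**

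Section 1.4 gives median survival of 13 to 44 months. I assume a median time to progression of 6 to 18 months and 5% to 20% of men dying without progression; neither is in the documents. The simulation draws exponential times and counts a death only if it comes without progression. One corner is incoherent and I set it aside: median progression of 18 months with median survival of 13.

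- With survival calls kept, about 18 to 30 of 30 deaths fall within 60 months.
- With withdrawal at progression, about 1 to 6 are seen.

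The second range is nearly the assumption itself: 30 × 0.05 = 1.5 and 30 × 0.20 = 6. A death between the first suspicious scan and its confirmation would add to it. It illustrates what happens if 5.1.4 governs and is not a forecast.

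**The case against.** The protocol, read as a whole, plainly intends survival follow-up. Section 3.6 orders it after progression, the schedule has a telephone-contact row, calls may go to family or the treating physician, and the synopsis counts the 5 years from the last study visit. On that reading, withdrawal in 5.1.4 means the end of treatment and visits, and survival contact goes on. For toxicity, 5.1.5.1 stops drug only, and footnote 4 keeps PSA going.

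Much of this stands. A reader might infer that the trial, followed as written, cannot answer its time-to-death objective, or that every man who progresses loses survival follow-up. The documents do not support either statement, because the same text expressly orders that follow-up. The loss arises only where 5.1.4 is allowed to override it.

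The 25.4% is also open to attack. It is an event frequency in melanoma, not a withdrawal rate. It includes skin events (4.2% at grade 3-4), for which 5.1.3 calls for skipped doses, and endocrine events (1.4%), which 5.1.5.2 can exempt. PSA is taken every 3 weeks in induction, so early responses would already be recorded. Section 1.3.6.1 adds that four phase 2 studies did not show the earlier suggested link between response and grade 3-4 IRAEs.

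The charitable reading still does not dispose of the conflict. Section 5.1.4 separates therapy from study in capitals. Its list includes withdrawn consent and study termination, where withdrawal does mean leaving. Section 5.1.5 already covers stopping the drug, and 6.2.1 provides no handover to PSA or survival contact. With two sites, two readings are plausible.

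**Conclusion.** The contradiction is real and lies in current text: 5.1.4 against 3.6, the synopsis, 6.4.2, footnote 4 of the schedule and 7.3.1, with 5.1.5 overlapping it. Its effect is conditional. Where a site applies 5.1.4 over the others, time to death is informatively censored at progression. Men withdrawn for toxicity then add nothing later to the primary endpoint, time to PSA progression or the IRAE correlations. PSA values and deaths before withdrawal remain usable.

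The size cannot be read from the documents. About 7.6 of 30 men is an upper-type proxy, and a reader should not infer that a quarter of the men will lose PSA follow-up. The power figures in the working rest on assumed f, toxicity unrelated to response and an assumed handling of missing men. The death counts rest on assumed progression times and an assumed share of deaths without progression. What is firm is the conflict itself and the absence of any analysis rule for men withdrawn under 5.1.4.

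**What to change.** Reconcile the passages by splitting 5.1.4 in two.

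1. **Reasons to stop ipilimumab:** the existing list, unchanged.
2. **Reasons to end follow-up:** withdrawal of consent to follow-up, termination of the study, and imprisonment or compulsory detention as now listed, unless the sponsor decides otherwise. The last must not drop out unnoticed, since exclusion criterion 7 in 4.2 also bars such men.

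Then state that men who stop ipilimumab for adverse events or illness stay on study for the PSA and scans already scheduled until radiographic progression, and that all men who progress go on to the calls in 3.6. Cross-refer 5.1.5, 6.2.1, footnote 4 and 7.3.1 to this wording.

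In 8.5, state how a man who leaves early is treated: whether he counts as a non-responder for the primary endpoint if no qualifying PSA was recorded, and where he is censored for each time-to-event endpoint. Align 8.4 with that rule.

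No treatment-stopping rule changes. The cost is a wording amendment and a few more PSA and scan visits for men off drug. These assessments are already scheduled; the documents do not show whether they are budgeted. Data not collected in the meantime may be impossible to recover.

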Patients with a life expectancy less than 6 months, treatment with any investigational agent in the last 28 days, more than 18 months since initiation of AST, or a concurrent active malignancy diagnosed within the last 5 years (other than non-melanoma skin cancer, or other readily treatable tumors with expected cure) will not be eligible for this study. Patients must not have a known autoimmune disease, use prednisone > 10 mg daily (or its equivalent) orally for any indication, or have chronic infections (including hepatitis B or C or HIV).

Criteria for Evaluation: (Efficacy, safety, stopping rules, etc.)

Patients will receive a history and physical exam and multiple laboratory tests (PSA, complete chemistry panel and blood counts, as well as tests for endocrinopathies) at baseline and every 3 weeks during the first 4 doses of therapy. Available labs (i.e. the chemistry panel and blood counts) will be reviewed prior to administration of ipilimumab. Imaging studies will be done at baseline, 12 weeks, 24 weeks and then every six months, or sooner if concerning symptoms arise. If there is no evidence of radiographic progression on the 24-week scan, patients will go on to receive four doses of maintenance ipilimumab therapy (weeks 24, 36, 48, 60). They will have a history and physical exam at least every three months. Their survival status will be assessed by phone survey every 6 months for up to five years after the last study visit.

Efficacy will be based on the results of the PSA and imaging studies (using PCWG2 and modified RECIST criteria). Safety will be monitored using the regular physician examinations and laboratory assessments.

Statistics:

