1.4 Overall Risk/Benefit Assessment melanoma and prostate cancer

Results from the 3 primary efficacy studies of ipilimumab suggest that the 10 mg/kg dose is active and offers the best benefit to risk ratio based on a 27.1% to 35.1% rate of disease control and a favorable 1-year survival rate of 48.6% to 59.1% compared with that reported in the literature (25.5% to 35%). ^{24,25,26,27} Substantial reductions in total tumor burden, including widely disseminated disease in the skin, lung, and/or other visceral

disease sites, were reported. More than half the responses were reported in subjects staged with M1b or M1c advanced melanoma disease, which is most resistant to approved therapies. The kinetics of ipilimumab resulted in known patterns of clinical activity (CR, PR and SD) as well as novel patterns, characterized by reductions in total tumor burden, including existing and new lesions, after initial tumor volume increase and/or after appearance of new lesions. In the pretreated population at 10 mg/kg in 2 of the 3 studies, disease control after initial tumor volume increase and/or new lesions was reported for 9.7% of subjects. Across all 3 studies, stable disease was often accompanied by clinically relevant reductions in tumor burden compared to baseline. All patterns of response, including SD, appeared to result in favorable survival, based on 1-year survival rates.

Characteristic organ-specific inflammatory IRAEs were reported with ipilimumab therapy, typically during induction therapy. IRAEs were mostly reversible within days to weeks following cessation of therapy or treatment with symptomatic therapy, corticosteroids or other anti-inflammatory agents, depending upon severity. Accumulated clinical experience resulted in detailed toxicity management guidelines (also termed algorithms), by use of which IRAEs can be effectively managed, especially when IRAEs are recognized early and subjects are treated in a timely fashion. This can minimize the occurrence of IRAE complications, such as GI perforation/colectomy or hepatic failure.

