3.5 End of Treatment Cycles

Patients who progress radiographically on ipilimumab after completion of the initial four doses will not receive more immunotherapy once progression has been documented. For soft-tissue lesions, the RECIST criteria for progression (see 6.4.2) will be used. For bone lesions, there should be ≥ 2 new lesions confirmed on a second scan at least 4 weeks later. Progression will not be assessed until completion of the initial 4 cycles of treatment in order to avoid premature discontinuation of therapy.

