5 STUDY THERAPY

All patients will receive ipilimumab 10 mg/kg IV over 90 minutes on day 1 of each 21-day cycle for four cycles. Those patients who have not progressed (radiographically) will also receive the same dose of ipilimumab once every three months for an additional four doses. Each patient's available lab results (i.e. chemistries and blood counts) will be reviewed prior to each ipilimumab infusion.

5.1 **Ipilimumab**

Each patient will receive ipilimumab 10 mg/kg IV over 90 minutes (not bolus or IV push).

Ipilimumab (BMS-734016) is a human immunoglobulin G (IgG1) κ anti-CTLA-4 monoclonal antibody (mAb). In vitro studies were performed with ipilimumab to demonstrate that it is specific for CTLA-4, actively inhibits CTLA-4 interactions with B7.1 and B7.2, does not show any cross-reactivity with human B7.1, B7.2 negative cell lines, and stains the appropriate cells without nonspecific cross-reactivity in normal human tissues, as demonstrated by immunohistochemistry. Ipilimumab does cross-react with CTLA-4 in non-human primates, including cynomolgus monkeys.

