6.4.3.1 Definition of Index Lesion Response Using mRECIST

* Complete Disappearance of all target lesions

Response (CR):

(SD):

* Partial Response At least a 30% decrease in the sum of the LD of target lesions,

taking as reference the baseline sum LD (PR):

* Progressive At least a 20% increase in the sum of the LD of target lesions, Disease (PD):

taking as reference the smallest sum LD recorded since the

treatment started or the appearance of one or more new

lesions

* Stable Disease Neither sufficient shrinkage to qualify for PR nor sufficient

increase to qualify for PD, taking as reference the smallest sum

LD since the treatment started

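### The protocol gives different confirmation rules for radiographic progression in 5.1.4, 3.5, 6.4.3 and the synopsis, so week-24 treatment status and the progression event are not uniquely defined

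*Combined protocol and SAP*

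**What the plan says.** The rules for radiographic progression are spread over several sections of the combined protocol and SAP.

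- **5.1.4 (discontinuation).** After 12 weeks of therapy, "all radiographic progression must be confirmed by a repeat scan done at least 4 weeks after the suspicious scan". No lesion type is exempt.
- **3.5 (end of treatment).** "For soft-tissue lesions, the RECIST criteria for progression (see 6.4.2) will be used". For bone, at least two new lesions are needed, "confirmed on a second scan at least 4 weeks later". No second scan is mentioned for soft tissue. The cross-reference goes to 6.4.2, although the progression criteria stand in 6.4.3.
- **6.4.3.1 (index lesions).** Progression is "At least a 20% increase in the sum of the LD of target lesions" relative to the smallest sum recorded, or a new lesion. It is met on one assessment.
- **6.4.3.2 and 6.4.3.3 (bone).** The first needs two or more new lesions on bone scan. The second treats new uptake as progression, with further imaging of the lesion rather than a repeat scan four weeks later.
- **Synopsis, study schema.** "Patients without progression at Week 24 will subsequently receive maintenance ipilimumab".
- **Synopsis, Criteria for Evaluation.** "If there is no evidence of radiographic progression on the 24-week scan, patients will go on to receive four doses of maintenance ipilimumab therapy".
- **Section 5.** "Those patients who have not progressed (radiographically) will also receive the same dose of ipilimumab once every three months".
- **8.5 (analysis).** Time to disease progression by any measure is estimated by Kaplan-Meier. Censoring reasons are listed, but 8.5 does not say whether a radiographic event must be confirmed or which scan dates it.

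**The concern.** The same scan can give a different answer depending on which section the reader follows. That matters in two places.

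The first is the week-24 decision, where maintenance depends on whether a man has progressed. The second is the secondary endpoint of time to disease progression, where both the event and its date depend on the confirmation rule.

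The second problem may not be repairable at analysis. Sections 3.3.2 and 6.1 continue scans only until radiographic progression, and 3.6 then moves follow-up to telephone surveys. If progression is called on one scan, the confirming scan may never be taken, and a confirmed-progression rule could not later be applied to every patient.

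**Working it through.** The plan states no figure on this point, so there is none to reproduce. The check sets the rules side by side and then does the timing arithmetic.

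**1. One patient, each rule.** Take a man whose soft-tissue index lesions first meet the 20% criterion on the week 23/24 scan.

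| Section followed | Status when the week-24 dose is due |
|---|---|
| 3.5 with 6.4.3.1 | Progressed |
| Synopsis (both places) and section 5 | Progressed; maintenance condition not met |
| 5.1.4 | Suspicious scan only; criterion not yet met |

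**2. Can confirmation arrive in time?** Inputs: scan at week 23/24 and dose at week 24 (6.1), dosing window of 3 days either way (6.1 footnote), confirmation at least 4 weeks later (5.1.4).

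- Last permitted dosing day: 24 × 7 + 3 = day 171.
- Week-23 scan: earliest confirmation at week 27, 27 × 7 = day 189; 189 − 171 = 18 days too late.
- Week-24 scan: earliest confirmation at week 28, 28 × 7 = day 196; 196 − 171 = 25 days too late.
- If the 3-day window is also allowed for the week-23 scan: 161 − 3 + 28 = day 186; 186 − 171 = 15 days too late.

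In no case is confirmation available when the dose is due.

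**3. The week-12 scan.** Confirmation is possible from week 16, and no dose falls between weeks 10 and 24, so there is no clash with dosing. The questions of event status and event date still arise.

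**4. Event date.** If the confirming scan dates the event, the date moves by at least 4 weeks. If the next scan in the 6.1 schedule (week 36) serves as confirmation of a week-24 scan, it moves by 36 − 24 = 12 weeks.

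**5. Event count.** The documents give neither the number of men with first soft-tissue progression at week 24 nor the share that a repeat scan would confirm. Both are assumed here. With k such men among 30, a share c confirmed, no other events and no censoring, the progression-free proportion is 1 − k/30 under a single-scan rule and 1 − kc/30 under a confirmed rule.

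| k | Single scan | c = 100% | c = 80% | c = 60% | c = 40% |
|---|---|---|---|---|---|
| 3 | 90% | 90% | 92% | 94% | 96% |
| 6 | 80% | 80% | 84% | 88% | 92% |
| 9 | 70% | 70% | 76% | 82% | 88% |
| 12 | 60% | 60% | 68% | 76% | 84% |

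The table shows how the estimate responds to the rule. It is not a forecast for this trial.

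**The case against.** The best defence is that the sections can be read together. Section 5.1.4 introduces its repeat scan as an added condition. Section 3.5 does not say that soft tissue needs no confirmation, and it stops treatment only once progression has been documented. The synopsis is a summary. On this view the plan merely needs harmonising. That reading is possible, but it does not settle week 24: 3.5 names confirmation for bone alone, and the synopsis acts on the 24-week scan itself.

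It is also fair that 5.1.4 is a discontinuation rule and does not define an endpoint. The endpoint problem comes from 6.4.3 using one assessment while 8.5 is silent. The endpoint counts progression by any measure, so the radiographic rule matters only where imaging determines the event. It is a single-arm estimate with no hypothesis test attached.

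Four stronger readings are tempting, and the documents do not support them.

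- **A count of affected men.** Section 1.4 says that "disease control after initial tumor volume increase and/or new lesions was reported for 9.7% of subjects", and 0.097 × 30 = 2.9 might suggest about 3 men. But that figure comes from pretreated melanoma, is not limited to growth after week 12, and measures later disease control rather than failure of a four-week repeat scan. Sections 3.5, 5.1.4 and 6.4.4 already set aside growth before week 12.
- **Different rules for different patients.** No section assigns patients to different rules. The texts conflict; how sites have applied them is not known.
- **Section 6.4.3 confirms only responses.** It does not. Section 6.4.3.2 asks for panel or study-chair review of progression in non-target lesions alone, and 6.4.3.3 asks for further imaging of new bone-scan lesions. Neither is the repeat scan of 5.1.4.
- **The missing week-28 scan is a defect.** A confirming scan is triggered by an event and need not be in the schedule. Section 6.4.2.2 allows extra assessments when progression is suspected.

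**Conclusion.** The inconsistency is real and can be seen in the text alone. For soft tissue, 5.1.4 requires a repeat scan that 3.5, 6.4.3.1, section 5 and the synopsis do not mention. For bone, 6.4.3.2 and 6.4.3.3 differ on the number of new lesions, and neither restates the four-week repeat of 3.5. Section 6.4.3.2 also defers to the PCWG2 recommendations, but the protocol does not reproduce a rule from them that would settle this.

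The firm quantitative result is the timing. Progression first seen at week 23/24 cannot be confirmed before week 27/28, so treatment status at the week-24 dose depends on the section followed. This rests only on the schedule and the four-week interval. The effect on the Kaplan-Meier estimate cannot be sized from the documents.

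The consequence is limited to a secondary endpoint and to maintenance exposure. The primary PSA endpoint and the sample size do not depend on it. The point should be corrected but does not undermine the main analysis.

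**What to change.** 1. Reconcile the synopsis (schema and Criteria for Evaluation), 3.5, 5, 5.1.4 and 6.4.3 so that soft tissue and bone each have one progression and confirmation rule, stated the same way throughout. The rules may differ by lesion type. Which clinical rule applies is for the sponsor to decide.
2. State consistently what a patient's treatment status is while confirmation is pending, in particular at week 24. This too is the sponsor's decision.
3. Correct the cross-reference in 3.5 so that it leads to the progression criteria.
4. In 8.5, say whether the endpoint uses confirmed progression, which scan dates the event (for example the first suspicious scan if it is later confirmed), and how unconfirmed progression is handled, including when no second scan was taken.
5. If the endpoint uses confirmed progression, make clear that imaging continues until the confirming scan.

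The cost is protocol wording and a short addition to 8.5. Any repeat scan that the reconciled text keeps is one that at least one section already asks for. The sample size and the primary analysis do not change.
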